5.5. Packaging and Labeling

DCC-2618 (ripretinib, ZL-2307) will be provided by the sponsor. The drug will be prepared to oral tablets containing 50 mg of the study drug and packaged in high density polyethylene (HDPE) bottles with child-resistant closures.

Sutent® (sunitinib malate) 12.5 mg oral capsules will be supplied in the original package in HDPE medicine bottles and repasted with labels by the sponsor.

5.6. Storage Condition of Study drug

DCC-2618 (ripretinib, ZL-2307) bottles must be sealed up and stored at 5°C - 25°C (41°F-77°F). Protect from high humidity and intensive sunshine (such as places close to shower cubicle in the bathroom). A deviation of 2°C-27°C (35.6°F-80.6°F) is allowed.

Please refer to the package insert for information of storage and disposal of sunitinib.

The study drug must be stored in a safety place with restricted access and temperature monitored at study site.

5.7. Study drug Compliance

To ensure compliance of the study drug, the investigator or designated personnel must monitor all administrations of the study drug by study site. At each visit, personnel of study site must review patients' compliance to the study drug and remind patients to take the study drug as required. Compliance should be assessed by continuously counting the study drug.

If the patient still doesn't comply with administration of the study drug after education, the investigator must contact and discuss with the sponsor to make the patient withdraw from the study.

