Confirmation of absence of progressive disease: if institutional independent radiologic reviewers confirm there is no progressive disease, the patient will continue to receive the study drug, unless there are medical needs requiring discontinuation of the study drug (that is, rapid progression or clinical worsening). If investigators confirm progression according to clinical worsening, imageological examination should be performed and reviewed by institutional independent radiologic reviewers to confirm whether the patient has progression. Basis for

confirming progression based on clinical worsening should be recorded in source documents and eCRF of patients. If the investigator confirms progressive disease according to "RECIST v1.1-GIST-specific Criteria", the investigator should wait for assessment and confirmation by the independent radiologic review and then terminate the patient's treatment. If the investigator doesn't hope to confirm by the independent radiologic review or hopes to terminate the patient's treatment according to progressive disease based on "RECIST v1.1-GIST-specific Criteria" before obtaining results of the independent radiologic review, it is necessary to discuss with the sponsor.

Radiographic examination of patients of various treatment groups should be performed according to the predetermined time and cycle will not be influenced by suspension or delay of treatment with the study drug. If the patient discontinues treatment for reasons other than progressive disease, death, withdrawal of consent and lost to follow-up, the patient should receive radiographic examination for tumor assessment according to the specified time interval after treatment withdrawal until progressive disease based on "RECIST v1.1-GIST -specific Criteria" or initiation of new anti-tumor therapy.

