6.10.2. Overall survival follow-up by telephone

All patients will be followed up until withdrawal of consent or death for any reason. After safety follow-up visit, patients will be contacted once every 2 months (\pm 10 days) to collect new information of anti-tumor therapy and OS data.

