6.11.10.2. Pregnancy

Patients who receive DCC-2618 (ripretinib, ZL-2307) must inform the investigator of any pregnancy during the study treatment and within 104 days after the last dose of DCC-2618 (ripretinib, ZL-2307). Patients who use sunitinib must inform the investigator of any pregnancy during the study treatment.

If female patient becomes pregnant during the study, treatment with the study drug should be discontinued immediately forever. If female partner of male patient becomes pregnant during the study, the patient must inform the investigator immediately. Male patients must promise to take acceptable contraceptive measures during the study until 104 days after the last dose of

CC-2618 (ripretinib, ZL-2307) or the last dose of sunitinib (to ensure fetus is not in contact with the study drug). The investigator must inform the sponsor within 1 work days after the study site is aware of pregnancy of patients (or partners).

If the patients is receiving DCC-2618 (ripretinib, ZL-2307) treatment, the patient or female partner of male patient must be followed up until end of pregnancy. If informed consent is obtained, infants must be followed up until 1 year after birth. Pregnancy itself is not an AE.

6.11.11. **AEs**

All AEs will be evaluated, recorded and reported according to Good Clinical Practice (GCP) of the International Conference on Harmonization (ICH). Chapter **Error! Reference source not found.** summarizes the definition, collection period, evaluation criteria, recording, grading and reporting procedure of AEs.

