- Death with unknown causes must be reported as SAE. The cause of death should be clarified with every effort in follow-up activities. Autopsy is crutial to assessment on the cause of death. If an autopsy is performed, the Sponsor should be notified of the autopsy report.

• Reporting and follow-up of AESI

AESI occurring in the reporting period should be reported to the sponsor within 24 hours of awareness. Follow-up on AESI will be pursued until they are recovered/resolved to the baseline level or clinically stable or the investigator and the sponsor consistently consider follow-up is not required. For the purpose of study analysis, events that are not recovered during the study report period should be recorded as persistent.

• Serious Unexpected Adverse Reactions (SUSARs)

If drug-related serious unexpected adverse reactions (SUSARs) occur, the sponsor or the authorized personnel designated by the sponsor will ensure expedited reporting to appropriate regulatory authorities or other investigators taking part in this study. In addition, the sponsor or the authorized personnel designated by the sponsor will be responsible for reporting SUSARs to the ethics committee.

Pregnancy

Effective contraception is required for both male and female subjects of childbearing potential who are treated with DCC-2618 (Ripretinib, ZL-2307) during the trial and for 104 days after discontinuation of study drug. If a subject is found to be pregnant following initiation of study treat, the study drug will be permanently discontinued and the subject will be withdrawn from the trial. If a partner of a male subject becomes pregnant during the study or within 104 days after the last dose of study drug, the investigator should be informed immediately. The pregnancy must be recorded on "Pregnancy Reporting Form" and reported by the investigator to the Sponsor via email within 24 hours of becoming aware of the event. At the same time, the pregnancy also must be recorded on eCRF. All pregnancies must be followed to conclusion to determine their outcome. If the outcome of the pregnancy meets SAE criteria (e.g.,

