8.2. End of Study

The main reason for termination or withdrawal form the study should be confirmed according to the following classification:

- Death
- Lost to Follow-up
- Termination of the study by the sponsor
- Patients will withdraw from the study

Patient withdrawal and replacement 8.3.

Patients will be not substituted in the study.

9. Statistical Consideration

9.1. **Determination of sample size**

This study will bridge foreign clinical trial (study INTRIGUE) to prove the efficacy of the investigational drug DCC-2618 (ripretinib, ZL-2307) is consistent in foreign population and Chinese population. In the study, no statistical test hypothesis is specified in advance. Statistical significance test for efficacy endpoint and multiplicity correction for multiple analysis populations will not be performed.

Approximately 98 subjects will be enrolled into the study and randomized to a test group and a control group in a 1:1 ratio. The sample size eatimation will be based on the same study hypothesis as foreign, that is, median progression-free survival (mPFS) is 9 months in the test group and 6 months in the control group. Hazard ratio (HR) of the test group to the control group is 0.667. If the study keeps \geq 50% of the overall effect size of study INTRIGUE, that is, point estimate of HR should be ≤ 0.833 , it will be considered that results of this study are consistent with those of study INTRIGUE. If 58 cases of PFS events occur, a 80% probability will be obtained and athe conclusion of consistency will be drawn with a probability of 80%. Assumeing the subjects annual drop-out rate of subjects of the total study population is 5%, approximately 98 subjects (49 for the test group and the control group, respectively) are enrolled within 7 months and followed up for 7 months, and 58 cases of PFS events will occur. Main Primary analysis based on ITT will be carried outperformed when 58 cases of PFS events occur and it is estimated that the data cutoff of the analysis will be 7 months after completing enrollment.

Zai Lab

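### Section 5.7 points persistently non-compliant patients out of the study, which conflicts with the imaging rule in 6.10.1 and leaves open whether their IRR scans continue

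*Combined protocol and SAP*

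**What the plan says.** **Non-compliance.** Section 5.7: if education fails, "the investigator must contact and discuss with the sponsor to make the patient withdraw from the study". The step is conditional on failed education and goes through the sponsor, but its stated object is leaving the study, not stopping drug.

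**Imaging after treatment stops.** Section 6.10.1, repeated in note 20 of Table 1: "If the patient discontinues treatment for reasons other than progressive disease, death, withdrawal of consent and lost to follow-up", then "the patient should receive radiographic examination for tumor assessment according to the specified time interval after treatment withdrawal until progressive disease" (or the start of new anti-tumour therapy).

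**Survival follow-up.** Section 6.10.2: "All patients will be followed up until withdrawal of consent or death for any reason".

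**End of treatment.** Section 8.1 lists reasons for stopping study drug, among them investigator's decision and pregnancy. For a patient who leaves the study other than at the patient's own request it requires an end-of-treatment visit, safety follow-up and survival follow-up. It does not mention scans.

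**End of study.** Section 8.2: "The main reason for termination or withdrawal form the study should be confirmed according to the following classification". The list has four entries: death, loss to follow-up, termination by the sponsor, and withdrawal by the patient. Section 8.3 allows no replacement.

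**Pregnancy.** Section 7.11: "the study drug will be permanently discontinued and the subject will be withdrawn from the trial". Section 6.11.10.2 says only that "treatment with the study drug should be discontinued immediately forever".

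**Analysis.** The ITT set is all randomised patients (9.3). The primary endpoint is IRR-assessed PFS, with event and censoring rules left to the SAP (9.5.5.1). Consistency with INTRIGUE is judged by a point estimate of HR at or below 0.833 with 58 events (9.1).

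**The concern.** A site that follows 5.7 to the letter takes a consenting patient out of the study. Section 8.1 then tells it to keep three kinds of contact, none of which is imaging. A site that follows 6.10.1 keeps scanning the same patient. The protocol does not say which instruction governs.

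This matters because PFS needs scans. A patient whose imaging stops can count as a PFS event only through death, and no censoring rule written later can recover scans that were never taken. Treatment is open-label (5.11), and persistent non-compliance can plausibly depend on arm and tolerability. The decision to remove is also made by investigator and sponsor knowing the arm. If removed patients progress at a different rate from those who stay, censoring them is informative and the HR compared with 0.833 is biased. Removal serves no analytic purpose either: section 9.3 already defines a supportive per-protocol set that excludes significant protocol deviations.

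**Working it through.** **1. The passages side by side, for a non-compliant patient who still consents**

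| Section | Study drug | Scans | Survival follow-up |
|---|---|---|---|
| 5.7 | not addressed separately | not addressed; patient leaves the study | not addressed |
| 6.10.1, Table 1 note 20 | stopped | continue to progression or new therapy | – |
| 6.10.2 | – | – | continues |
| 8.1 | stopped | not named | continues |
| 8.2 | – | no exit category fits | no exit category fits |

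Only 5.7 points out of the study, and 8.1 does not restore the scans.

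**2. The plan's own figure.** Inputs from 9.1: assumed HR 0.667, cutoff 0.833, 58 events, 1:1 allocation. With SE(ln HR) = 2/√58 = 0.263:

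P(HR ≤ 0.833) = Φ[(ln 0.833 − ln 0.667) × √58 / 2] = Φ(0.222 × 3.808) = Φ(0.846) = 80.1%.

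This reproduces the stated 80%. Expected events at month 14 (exponential PFS with medians 9 and 6 months, 49 per arm, uniform 7-month accrual, 7 months of follow-up, 5% annual drop-out) come to 59.8, close to the stated 58.

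**3. Loss unrelated to prognosis.** If total drop-out were 30% a year instead of 5%, expected events at month 14 would be 53.7 and the probability 79.2%. Waiting for 58 events would take about 8.95 months of follow-up instead of 7. Precision is therefore not the issue.

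**4. Informative loss (illustration).** The documents give no expected number of non-compliant patients, so the rate, timing and hazard here are all assumptions: a share of one arm is non-compliant and has twice the usual hazard after month 2. Other settings are as in step 2, with the cut at month 14, 5000 simulated trials per scenario and an unstratified Cox HR. Each scenario compares full follow-up with censoring those patients at month 2.

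| Share and arm | Median HR, full follow-up | Median HR, removed | Shift | P(HR ≤ 0.833) |
|---|---|---|---|---|
| 5%, sunitinib | 0.650 | 0.666 | +0.016 | 83% to 80% |
| 10%, sunitinib | 0.635 | 0.664 | +0.029 | 85% to 79% |
| 10%, ripretinib | 0.702 | 0.666 | −0.036 | 75% to 81% |

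Ten per cent of an arm is about 5 patients (0.10 × 49 = 4.9). In the 10% sunitinib case the mean number of events falls from 60.7 to 57.5, a loss of about 3.

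In every row the HR after removal sits near the planning value of 0.667. Removal hides what happened to the removed patients; it does not push the estimate away from the planning assumption.

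**5. Pregnancy.** Section 7.11 treats stopping drug and leaving the trial as two steps and requires both. Section 6.11.10.2 requires only the first, 8.1 lists pregnancy as a reason for ending treatment, and 8.2 has no matching exit. This is a contradiction in the text; no arithmetic applies.

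**The case against.** The best counter-reading is that the protocol uses study withdrawal loosely. Section 8.1 is headed as end of treatment, yet speaks of patients who withdraw from the study and still requires visits and survival contact. On that reading 5.7 means ending treatment, 8.1 records it as an investigator's decision, 6.10.1 keeps the scans, and 8.2 needs no further category. Section 5.7 also requires a discussion with the sponsor, so removal is not automatic. These points stand. They show that scan loss is the literal reading of 5.7 but not the only one, so the defect is an unresolved conflict.

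A reader might go further in four ways that the documents do not support:

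- **That these patients do lose their scans.** No passage says so, and 6.10.1 and note 20 say the reverse.
- **That pregnancy removals are treatment-related.** Nothing links pregnancy to arm or tolerability, so 7.11 is an inconsistency only.
- **That removal pulls the probability of a consistency conclusion below plan.** The fall from 85% to 79% starts from a baseline raised by the assumed doubled hazard on sunitinib. It ends about where the plan already stands, at 80%. On ripretinib the movement is upward.
- **That ITT is undone.** All randomised patients stay in the set and their data to the last scan count. How they are censored depends on SAP rules that the protocol does not give.

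The illustrated shifts are also small beside the sampling error of 0.263 on the log scale. That limits the size of the concern but does not remove it: bias does not average out, and consistency is judged on a point estimate.

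**Conclusion.** The point holds as a contradiction to be resolved, worth fixing because it touches the primary endpoint. Section 5.7 taken literally, with 8.1, ends imaging for a consenting patient, while 6.10.1, note 20, 6.10.2 and 8.2 point the other way. If sites followed 5.7, IRR-PFS could be censored informatively. The illustrated shift is about 0.03 to 0.04 in HR with 10% of one arm removed, and about 0.016 with 5% of the sunitinib arm. For scale, the planning HR and the cutoff are 0.166 apart (0.833 − 0.667). The direction depends on the arm: removals on sunitinib move the HR towards 1, and removals on ripretinib move it away from 1, which makes a consistency conclusion easier to reach. These sizes rest wholly on the assumed rate, month-2 timing and doubled hazard. The pregnancy passages are a separate inconsistency that carries no bias claim.

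**What to change.** Reconcile 5.7 with 6.10.1 (and Table 1 note 20), 6.10.2, 8.1 and 8.2. State in separate sentences what happens to study drug and what happens to study follow-up. On follow-up, say that a non-compliant patient who has not withdrawn consent stays in the study for scheduled IRR imaging under 6.10.1 and for survival follow-up. Add imaging to the follow-up named in 8.1, by reference to 6.10.1, so the two sections agree. The decision on study drug in such patients remains with the sponsor and investigators.

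Separately, reconcile 7.11 with 6.11.10.2, 8.1 and 8.2 on whether a pregnant subject leaves treatment only or the trial as well. No imaging rule is proposed for that case.

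The cost is a few sentences in an amendment, plus scans that 6.10.1 already schedules.

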5.8. Counting of Study drug

The investigator is responsible for counting the study drug at study site. The investigator must ensure administration of the study drug only in compliance with the study protocol. If conditions allow, the investigator can assign the responsibility of counting the study drug to pharmacist or other appropriate personnel. Record of drug counting must be kept by clinical study site and the followings should be described in record: date of the study drug sent to study site, inventory of the study drug at study site, amount of the study drug distributed to each patient, amount of the study drug returned by each patient, amount of the study drug returned

Dose adjustment principle of laboratory abnormality is based on laboratory test results of study institution.

to the sponsor and amount of the study drug destructed at study site Counting record should include date, amount, bottle number and patient number. Study monitor should continuously review drug accountability at study site during visit. The sponsor should be informed of any distribution mistake or deviation immediately.

Patients must be told to return all bottles of unused, partially used and used study drugs to study site at each visit. Throughout the study, study monitor must verify record and inventory of the study drug.

5.9. Disposal, Return or Keep of the Unused Study drugs

Patients must be told to return all bottles of used, partially used and unused study drugs. Personnel of study site or pharmacy personnel (if applicable) must keep all materials returned by patients until they are returned to the sponsor or destructed by study site. If the study drug is destructed at study site, the investigator or designated personnel must ensure to destruct these materials according to applicable environmental protection law and regulations, institutional policies and any special instructions provided by the sponsor. Destruction must be recorded in detail.

5.10. Method for Assigning Subjects into Treatment Groups

Patients will be randomized at 1:1 to DCC-2618 (ripretinib, ZL-2307) 150 mg group or sunitinib 50 mg group. Patients with KIT/PDGFRA WT GIST (KIT and PDGFRA wild-type, regardless of status of any other gene mutations) accounted for at most 10% of all enrolled patients. Stratification factors of randomization include:

• KIT exon 11 mutation; KIT exon 9 mutation; other (KIT/PDGFRA WT or other KIT [lacking exon 9 or 11]/PDGFRA mutation);

5.11. Blinding and Unblinding

This is an open-label study and doesn't involve blinding and unblinding.

5.12. Past and Concomitant Treatment

5.12.1. Previous medications/treatment

Any information of all medications (including vitamin supplementation, over the counter medications and oral herbal preparations) or non-drug treatments used within 30 days prior to signing the informed consent form and prior to the first dose of the study drug should be recorded in source documents and electronic Case Report Form (eCRF) of patients.

5.12.2. Prior Anti-Tumor Therapy

Any prior anti-tumor drugs and non-drug treatments should be recorded in source documents and eCRF of patients.

5.12.3. Concomitant medication

Any medications (including vitamin supplementation, over the counter medications and oral herbal preparations) or non-drug treatments used in the period from the first dose of the study drug to 30 days (including 30 days) after the last dose of the invstigational drug should be recorded in source documents and eCRF of patients.

5.12.3.1. Drugs Allowed to be Used

Patients can use drugs that can relieve symptoms (such as analgesics, laxatives and antiemetics) as long as they are not prohibited by the study protocol.

The drug restrictions are not applicable to sunitinib. Please refer to the approved package insert for information of sunitinib.

5.12.3.2. Prohibited Drugs and Substances

Prohibited drugs and some food are not allowed from the screening period to safety follow-up visit. Except for the study drug, anti-tumor therapies that have an inhibitory effect or potential inhibitory effect on GIST are prohibited during the study.

All patients should abide by the following criteria of prohibited drugs before randomization.

- Receive imatinib treatment within 10 days prior to the first dose of the study drug or any other anti-tumor drugs or therapies for advanced GIST.
- Potent or moderate inhibitors or inducers of CYP3A4, including some herbal medicines (e.g., St. John's wort) should be discontinued 14 days (or 5 x half-life, whichever is longer) prior to the first dose of the study drug.
 - For guidance of CYP3A4 enzyme inhibitor, please refer to the website of the Indiana University, School of Medicine: (http://medicine.iupui.edu/clinpharm/ddis/main-table/).
- Grapefruit or grapefruit juice should be prohibited within at least 14 days prior to the first dose of the study drug.
- Known BCRP transporter substrate or inhibitor: discontinue within at least 14 days or 5 half-lives (whichever is longer) prior to the first dose of the study drug.
 - For information of BCRP inhibitors and substrates, please refer to Food and Drug Administration (FDA) website:
 - http://www.fda.gov/Drugs/DevelopmentApprovalProcess/DevelopmentResources/DrugInteractionsLabeling/ucm093664.htm.

After randomization and during the study, patients randomized to the sunitinib group will follow requirements for prohibited drugs specified in the approved package insert.

The following are prohibited after randomization and during the study for patients randomized to DCC-2618:

- Strong and moderate inducers of CYP3A, including certain herbal medications (e.g. St. John's Wort)
- 5.12.3.3. Please refer to the Indiana University Department of Medicine website (http://medicine.iupui.edu/clinpharm/ddis/main-table/) for guidance on medications that induce CYP3A4 enzymes.Drugs to be avoided or used with caution

Patients who use DCC-2618 (ripretinib, ZL-2307) should avoid the following drugs or use the following drugs with caution after discussing with the sponsor (provide updated information to study site during the study):

- Strong or moderate inhibitors of CYP3A including grapefruit juice.
- Known substrates or inhibitors of BCRP transporters and P-glycoprotein 1 (permeability glycoprotein, also known as MDR1). Please refer to the FDA's website for inhibitors https://www.fda.gov/Drugs/DevelopmentApprovalProcess/DevelopmentResources/DrugI nteractionsLabeling/ucm093664.htmMedications dependent on CYP2C8 for their metabolism. Please refer to the Indiana University Department of Medicine website

Zai Lab

(http://medicine.iupui.edu/clinpharm/ddis/main-table/) for guidance on these medicines.

0

For patients who use any of the above drugs, any potential drug interaction with DCC-2618 (ripretinib, ZL-2307) should be closely monitored.

Please refer to the approved package insert for drug interaction of sunitinib.

